Summaries for CBCL 6-18 will be presented overall for all applicable study participants and additionally based on the subject's age at time of entry into study SP848, using the following age groups:

- $\geq 6$  to  $< 12$  years
- $\geq 12$  to  $< 16$  years
- Total  $\geq 6$  to  $< 16$  years
- $\geq 16$  years

Summaries for BRIEF-P will be presented overall for all applicable study participants and additionally based on the subject's age at time of entry into study SP848, using the following age groups:

- $\geq 2$  to  $< 4$  years
- $\geq 4$  to  $< 5$  years

Summaries for BRIEF will be presented overall for all applicable study participants and additionally based on the subject's age at time of entry into study SP848, using the following age groups:

- $\geq 5$  to  $< 12$  years
- $\geq 12$  to  $< 16$  years
- Total  $\geq 5$  to  $< 16$  years
- $\geq 16$  years

Summaries for Bayley-III assessments will be presented overall for all applicable study participants and additionally based on the subject's age at time of entry into study SP848, using the following age groups:

- $\geq 1$  to  $< 6$  months
- $\geq 6$  months to  $< 1$  year
- $\geq 1$  year to  $< 18$  months

All summaries will be descriptive; no statistical hypothesis testing is planned.

A complete set of listings containing all documented data and all calculated data (e.g., change from Baseline) will be generated, and will be sorted by site, subject number and visit (where applicable).

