### **3.2.23 Hospital stay duration**

The duration of each hospital stay will be calculated as the discharge date minus the admission date (Hospitalization/Emergency Room [ER] Visit Date on the CRF/eCRF module) plus 1 day for hospital stays with a discharge date.

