#### **10.4.2 Hospital stays and ER visits**

The number of hospital stays per subject during the Treatment Period will be summarized. The number of hospital stays will be summarized using the categories 0, 1, 2, 3, 4, and 5 or more. The number and percentage of study participants with specific reasons for duration of hospital stays will be summarized for the duration of the Treatment Period.

The durations of hospital stays for the Treatment Period will be summarized. Duration of hospital stays (as defined in Section 3.2.23) will be categorized as 0 days, 1-5 days, 6-10 days, 11-15 days, and >15 days, and summarized for the duration of the Treatment Period.

An event logged on the Hospitalization/ER Visit CRF/eCRF module where ER is marked as initial entry point will be defined as an ER visit. An ER visit with a subject transfer to an inpatient general ward will also be counted as a hospitalization. However, all other instances of ER visits (where subject transfer is not to an inpatient general ward) will not be counted as hospitalizations. Descriptive statistics for the number of ER stays during the Treatment Period will be presented. The number of ER visits will be summarized using the categories 0, 1, 2, and 3 or more. The number and percentage of study participants with specific reasons for duration of ER visits will be summarized for the duration of the Treatment Period.

Hospitalizations with either a partial admission or discharge date are ignored for the calculation of duration of hospital stay. However, such hospitalizations are counted for the number of hospital stays. Study participants with no hospital stays will have a duration of 0 days. Should distinct records for hospital stays overlap, then the days during the overlap will only be counted once. Similarly this also applies for ER visits.

All hospitalization and ER data will be listed.

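### Section 10.4.2 leaves ER-entry stays in inpatient units other than a general ward out of the hospital-stay count and duration, and can record them as 0 days

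*SAP*

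**What the plan says.** Section 10.4.2 classifies events on the Hospitalization/ER Visit module in three steps.

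- An event "where ER is marked as initial entry point will be defined as an ER visit".
- One route leads from there to a hospitalization: "An ER visit with a subject transfer to an inpatient general ward will also be counted as a hospitalization".
- The rule is then closed: "all other instances of ER visits (where subject transfer is not to an inpatient general ward) will not be counted as hospitalizations".

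The same section sets the value for participants without a counted stay, "Study participants with no hospital stays will have a duration of 0 days", and says that duration "will be categorized as 0 days, 1-5 days, 6-10 days, 11-15 days, and >15 days". Section 3.2.23 defines the length of a stay: "The duration of each hospital stay will be calculated as the discharge date minus the admission date", plus 1 day, with the date on the Hospitalization/ER Visit module as the admission date.

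Section 10.4.2 ends with "All hospitalization and ER data will be listed". Section 2.3.4.3 places health care resource use among the other efficacy variables, below the secondary ones. Section 3.1 states "All summaries will be descriptive; no statistical hypothesis testing is planned".

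**The concern.** The rule is evidently meant to separate ER visits that lead to admission from those that do not. As written, it separates them by type of ward. A participant who enters through the ER and stays in intensive care or a specialist unit has been an inpatient, yet falls under the exclusion unless a general-ward transfer is recorded. No other section makes an exception.

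This has two consequences. First, the entry route decides whether the same stay is counted: the exclusion applies only to ER-entry events, so it does not reach an intensive-care stay that began without the ER. Second, the 0-day category, meant for participants who were never in hospital, can include participants who were.

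What is at stake is the accuracy of the hospital-stay count and duration tables. An epilepsy study that accepts participants who left SP847 because of status epilepticus (Section 2.1) can reasonably expect some events of this kind.

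**Working it through.** The plan gives no figure to reproduce, and no power or sample size calculation is involved. The check applies the counting rule of Section 10.4.2 and the duration formula of Section 3.2.23 to example events.

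**Inputs from the SAP**

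- An ER-entry event counts as a hospitalization only with transfer to a general ward (Section 10.4.2).
- Duration = discharge date − admission date + 1 (Section 3.2.23). The smallest value for a fully dated stay is therefore 0 + 1 = 1 day.
- No counted stay means 0 days (Section 10.4.2).
- Categories are 0, 1-5, 6-10, 11-15 and >15 days (Section 10.4.2).

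**Assumed inputs.** The dates and care pathways below are examples, not SAP data. In each, the event is the participant's only one.

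| Example | Actual length by Section 3.2.23 | Under Section 10.4.2 as written |
|---|---|---|
| ER entry, intensive care only, day 1 to day 10 | 10 − 1 + 1 = 10 days (6-10) | 0 stays, 0 days, 1 ER visit |
| ER entry, intensive care only, day 1 to day 16 | 16 − 1 + 1 = 16 days (>15) | 0 stays, 0 days, 1 ER visit |
| ER entry, intensive care, then a recorded general-ward transfer, day 1 to day 10 | 10 days (6-10) | 1 stay, 10 days, 1 ER visit |
| ER entry, sent home without admission | not an inpatient stay | 0 stays, 0 days, 1 ER visit |

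More generally, for an assumed inpatient length L from 1 to 20 days with no general-ward transfer, the rule returns 0 where the formula gives L. The lost days therefore run from 1 to 20, and the correct category runs from 1-5 to >15.

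**What follows**

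1. Rows 1 and 4 produce the same hospital-stay output. Since a counted, fully dated stay is at least 1 day, 0 days is the value for no counted stay, and the rule puts a 10-day inpatient stay there.
2. If the participant has another counted stay, the result is understated rather than zero. With an additional, non-overlapping counted stay of 3 days (assumed), the participant has 1 stay and 3 days instead of 1 + 1 = 2 stays and 3 + 10 = 13 days.
3. The rule removes inpatient stays and adds none, so the error has one direction: downward.
4. The ER tables do not recover the lost days. Section 3.2.23 defines duration for hospital stays only, and Section 10.4.2 gives length categories for hospital stays but none for ER visits. The days remain visible only in the listings.

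**The case against.** The strongest objection is that the rule depends on fields of a form that the SAP does not show. If a general ward is the only inpatient destination that can be ticked, the rule merely separates admitted from non-admitted ER visits, and nothing is lost. That possibility stands. It limits what can be said about frequency, but the written rule still turns on the kind of ward, and a programmer following it would exclude an intensive-care transfer wherever one is recorded.

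A reader might infer that the most severe admissions are dropped as a class. The SAP does not support this. It does not mention intensive care in this rule, the other destinations need not be severe, and the exclusion correctly covers ER visits without admission. Nor does the wording require the general-ward transfer to be direct or to come first, so a participant who later steps down to a general ward can qualify with the full stay counted.

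A reader might also try to size the loss by assuming that, say, 10% to 30% of ER-entry admissions go to other units. The result would be a loss of 10% to 30% of those stays, which is the assumption restated; nothing in the SAP supports any particular share.

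It is also fair to say that these events do not vanish. They count as ER visits, reasons are summarized, all records are listed, and any reported as serious adverse events appear in the Section 8.2 tables. Safety conclusions do not rest on the resource-use table. This bears on importance and does not make the hospital-stay summaries correct.

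Finally, simply adding transfer to another hospital as a qualifying destination would create a new error: a move between two ERs without admission would count, and an episode logged on two records could count as two stays. The existing overlap rule removes duplicate days, not duplicate stays. The fix below allows for this.

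**Conclusion.** The point holds within limits. Under the literal rule, an ER-entry stay in a non-general inpatient unit, with no recorded general-ward transfer, is omitted from the number and duration of hospital stays; it gives 0 days if the participant has no other counted stay, and understated totals otherwise. The effect per event is the whole stay: 10 days in the main example, and 1 to 20 days over the assumed range. The effect on the study summaries is downward but cannot be quantified, because the number of affected events and the form's transfer options are not in the SAP.

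The affected outputs are descriptive resource-use tables. Primary safety variables (Section 2.3.1) and secondary efficacy variables (Section 2.3.4.2) are unaffected. The conclusion assumes only that the module can record an inpatient destination other than a general ward. Correcting the rule is worthwhile because it gives a wrong value for any such event and costs little to change.

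**What to change.** Replace the ER-to-hospitalization rule in Section 10.4.2 with wording such as:

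> An ER visit followed by transfer to any inpatient unit recorded on the Hospitalization/ER Visit module (general ward, intensive care or other inpatient unit) is also counted as a hospitalization, with duration per Section 3.2.23; only ER visits without inpatient admission are excluded. A transfer to another hospital counts only if it results in inpatient admission, and contiguous records of the same episode are counted as one stay.

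The cost is this change of text and one derivation. The derivation must be checked against the module's transfer options; if a general ward turns out to be the only inpatient option, a sentence saying that it stands for any inpatient admission is enough. Reported stay counts and durations may rise slightly. The ER visit counts need not change.

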## 12 APPENDICES

### 12.1 Marked abnormality criteria for laboratory data

#### 12.1.1 Marked abnormality criteria for hematology data

**Table 12–1: Hematology abnormality criteria**

Parameter	Age Range	Unit (conventional)	Abnormality criteria (conventional unit)	Unit (standard)	Abnormality criteria (standard unit)
Hematocrit	<2y	%	≤27 >45	%	≤27 >45
	2y - <17y	%	≤29 >47	%	≤29 >47
	≥17y	%	≤85% of LLN ≥115% of ULN	%	≤85% of LLN ≥115% of ULN
Hemoglobin	<2y	g/dL	≤9.0 >15.0	g/L	≤90 >150
	2y - <17y	g/dL	≤9.5 >16.0	g/L	≤95 >160
	≥17y	g/dL	≤85% of LLN ≥115% of ULN	g/L	≤85% of LLN ≥115% of ULN
WBC/ Leukocytes	All	10  /L	≤3.0 ≥16.0	G/L	≤3.0 ≥16.0
Lymphocytes Absolute	<2y	10  /L	<1.0 >9.8	G/L	<1.0 >9.8
	2y - <6y	10  /L	<0.7 >6.9	G/L	<0.7 >6.9
	≥6y	10  /L	<0.6 >5.0	G/L	<0.6 >5.0
Basophils	>1m	%	≥5.0	%	≥5.0
Basophils Absolute	>1m	10  /L	≥0.4	G/L	≥0.4
Eosinophils	>1m	%	≥10	%	≥10
Eosinophils Absolute	>1m	10  /L	≥1.0	G/L	≥1.0
Monocytes	>1m	%	≥20.0	%	≥20.0

**Table 12–1: Hematology abnormality criteria**

Parameter	Age Range	Unit (conventional)	Abnormality criteria (conventional unit)	Unit (standard)	Abnormality criteria (standard unit)
Monocytes Absolute	>1m	10  /L	≥2.0	G/L	≥2.0
Neutrophils Absolute	>1m	10  /L	<1.5	G/L	<1.5
Platelets	>1m	10  /L	≤100 ≥600	G/L	≤100 ≥600
RBC/ Erythrocytes	<2y	10  /L	<3.0	T/L	<3.0
	≥2y	10  /L	<3.5	T/L	<3.5

Abbreviations: ANC=absolute neutrophil count; m=months, y=years. A month is defined as 28 days; a year is defined as 365.25 days.

This document cannot be used to support any marketing authorization application and any extensions or variations thereof.

**12.1.2 Marked abnormality criteria for chemistry data**

**Table 12–2: Chemistry abnormality criteria**

Parameter	Age Range	Unit (conventional)	Abnormality criteria (conventional unit)	Unit (standard)	Abnormality criteria (standard unit)
AST (SGOT)	All	U/L	≥3.0 x ULN ≥5.0 x ULN ≥10.0 x ULN	U/L	≥3.0 x ULN ≥5.0 x ULN ≥10.0 x ULN
ALT (SGPT)	All	U/L	≥3.0 x ULN ≥5.0 x ULN ≥10.0 x ULN	U/L	≥3.0 x ULN ≥5.0 x ULN ≥10.0 x ULN
Alkaline Phosphatase	<4y	U/L	≥690	U/L	≥690
	4y - <10y	U/L	≥834	U/L	≥834
	10y - <17y	U/L	≥1761	U/L	≥1761
	≥17y	U/L	≥3.0 x ULN	U/L	≥3.0 x ULN
GGT	<6m	U/L	≥522	U/L	≥522
	6m - <1y	U/L	≥279	U/L	≥279
	1y - <13y	U/L	≥66	U/L	≥66
	13y - <17y	U/L	≥126	U/L	≥126
	≥17y	U/L	≥3.0 x ULN	U/L	≥3.0 x ULN
Total Bilirubin	>1m	mg/dL	≥2.0	umol/L	≥34.208
Total Protein	2m-<1y	g/dL	<3.0 >11.9	g/L	<30 >119
	1y - <17y	g/dL	<4.3 >12.0	g/L	<43 >120
	≥17y	g/dL	<4.3 >13.0	g/L	<43 >130
Albumin	<1y	g/dL	<1.6 >7.2	g/L	<16 >72
	≥1y - <17y	g/dL	<2.4 >8.4	g/L	<24 >84
	≥17y	g/dL	<2.6	g/L	<26
BUN	<1y	mg/dL	≥24	mmol/L	≥8.568
	1y - <17y	mg/dL	≥36	mmol/L	≥12.852

**Table 12–2: Chemistry abnormality criteria**

Parameter	Age Range	Unit (conventional)	Abnormality criteria (conventional unit)	Unit (standard)	Abnormality criteria (standard unit)
	≥17y	mg/dL	≥40	mmol/L	≥14.28
Urea	<1y	mg/dL	>42	mmol/L	>7.014
	≥1y	mg/dL	>60	mmol/L	>10.02
Creatinine	1y - <10y	mg/dL	>1.2	umol/L	>106.8
	10y - <16y	mg/dL	>1.8	umol/L	>159.12
	≥16y	mg/dL	≥2.0	umol/L	≥176.8
Creatinine Clearance a b	All	mL/min	<50	mL/s	<0.835
Bicarbonate	>1m - <17y	mEq/L	<15 >38	mmol/L	<15 >38
	≥17y	mEq/L	<18 >38	mmol/L	<18 >38
Calcium	<1y	mg/dL	<6.9 >12.2	mmol/L	<1.725 >3.05
	1y - <17y	mg/dL	<7.4 >11.7	mmol/L	<1.85 >2.925
	≥17y	mg/dL	≤7.6 ≥11.0	mmol/L	≤1.9 ≥2.75
Chloride	>1m	mEq/L	≤90 ≥112	mmol/L	≤90 ≥112
Phosphorous	<1y	mg/dL	<1.8 >8.2	mmol/L	<0.5814 >2.6486
	1y - <17y	mg/dL	<1.8 >7.4	mmol/L	<0.5814 >2.3902
	≥17y	mg/dL	≤2.0 ≥6.0	mmol/L	≤0.646 ≥1.938
Potassium	<1y	mEq/L	≤3.0 ≥6.5	mmol/L	≤3.0 ≥6.5
	≥1y	mEq/L	≤3.0 ≥6.0	mmol/L	≤3.0 ≥6.0

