**Table 12–2: Chemistry abnormality criteria**

Parameter	Age Range	Unit (conventional)	Abnormality criteria (conventional unit)	Unit (standard)	Abnormality criteria (standard unit)
Sodium	>1m	mEq/L	<127 >151	mmol/L	<127 >151
Glucose	>1m - <17y	mg/dL	<50 ≥180	mmol/L	<2.775 ≥9.99
	≥17y	mg/dL	<50 ≥200	mmol/L	<2.775 ≥11.1
Total Cholesterol	≥1y	mg/dL	>250	mmol/L	>6.475
LDL (calculated)	1y - <17y	mg/dL	>140	mmol/L	>3.626
	≥17y	mg/dL	>200	mmol/L	>5.18
HDL	≤2y	mg/dL	<10	mmol/L	<0.259
	>2y	mg/dL	<20	mmol/L	<0.518
Triglycerides	<1y	mg/dL	>750	mmol/L	>8.475
	≥1y	mg/dL	>300	mmol/L	>3.39
Uric Acid	<1y	mg/dL	>7.7	umol/L	>457.996
	1y - <13y	mg/dL	>6.5	umol/L	>386.62
	13y - <17y	mg/dL	>8.6	umol/L	>511.528
	≥17y	mg/dL	>9.5	umol/L	>565.06
Thyroxine (T4)	<1y	ug/dL	≤4.3 ≥18.4	nmol/L	≤55.3453 ≥236.8264
	≥1y	ug/dL	≤3.8 ≥13.5	nmol/L	≤48.9098 ≥173.7585
Globulin	<1y	g/dL	<1.0 >4.5	g/L	<10 >45
	≥1y	g/dL	<1.2 >5.3	g/L	<12 >53

Abbreviations: ALT= alanine aminotransferase; AST=aspartate aminotransferase; BUN=blood urea nitrogen; dL=deciliter; GGT: gamma-glutamyl transferase; HDL=high density lipoprotein; LDL=low density lipoprotein; L=liter; m=months (a month is defined as 28 days) mg=milligram; mmol=millimoles; µg=microgram; U=unit; ULN=upper limit of normal; y=years (a year is defined as 365.25 days)

aSchwartz equation (study participants <12): Cr Cl ml/min=[Height (cm) \* 0.55] / serum creatinine

---

b Cockcroft equation (study participants >12): Male: Cr Cl ml/min= $[(140-\text{age}) \times \text{body weight (kg)}] / (72 \times \text{serum creatinine})$ ; Female: Cr Cl ml/min= $[(140-\text{age}) \times \text{body weight (kg)}] / (72 \times \text{serum creatinine}) \times 0.85$

This document cannot be used to support any marketing authorization application and any extensions or variations thereof.

REDACTED COPY

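### Table 12–2 holds inconsistent renal limits: BUN and urea differ for the same mmol/L quantity, one creatinine conversion is slightly off, and the clearance equations do not meet at age 12

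*SAP*

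**What the plan says.** Section 8.3 of the SAP counts participants with treatment-emergent markedly abnormal (TEMA) laboratory values at each post-Baseline visit and at Last Visit, and takes the criteria from Appendix 12.1. For chemistry these are in Table 12–2, which gives each limit in conventional and standard units.

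- **BUN:** "BUN <1y mg/dL ≥24 mmol/L ≥8.568", then "1y - <17y mg/dL ≥36 mmol/L ≥12.852", then "≥17y mg/dL ≥40 mmol/L ≥14.28".
- **Urea:** "Urea <1y mg/dL >42 mmol/L >7.014", then "≥1y mg/dL >60 mmol/L >10.02".
- **Creatinine:** "Creatinine 1y - <10y mg/dL >1.2 umol/L >106.8". The next two rows give 1.8 mg/dL as 159.12 umol/L and 2.0 mg/dL as 176.8 umol/L.
- **Creatinine clearance:** one limit, below 50 mL/min, for all ages. Footnote a reads "Schwartz equation (study participants <12" and footnote b reads "Cockcroft equation (study participants >12".

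The table's abbreviations define BUN as blood urea nitrogen. The SAP does not say which of BUN and urea governs, or which equation applies at age 12.

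**The concern.** BUN and urea are two ways of reporting one measurement. In mg/dL they differ, because one is the mass of nitrogen and the other the mass of the whole molecule. Once each is converted to mmol/L of urea, a single concentration should meet a single limit in a given age band. Table 12–2 gives two, and the age bands also differ: BUN is split at 17 years and urea is not. Where results arrive under both names, the flag would follow the label on the result and not the concentration.

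The other two points are of the same kind but smaller. A standard-unit limit that does not equal its conventional-unit limit can flag a result in one unit system and not in the other. A derived parameter with no equation for some participants has no value for them. Section 8.3 bases percentages on participants with a value, so they would leave both the numerator and the denominator.

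**Working it through.** **Inputs.** All limits come from the current text of SAP Table 12–2 and its footnotes. One assumption from outside the document is used: molar masses of 60.06 g/mol for urea and 28.014 g of nitrogen per mol of urea.

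**Step 1. Factor implied by each row** (standard-unit limit ÷ conventional-unit limit):

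- BUN: 8.568/24 = 0.357; 12.852/36 = 0.357; 14.28/40 = 0.357.
- Urea: 7.014/42 = 0.167; 10.02/60 = 0.167.
- Creatinine: 106.8/1.2 = 89.0; 159.12/1.8 = 88.4; 176.8/2.0 = 88.4.

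Every BUN and urea conversion reproduces exactly. Among the renal conversions checked here, only the first creatinine row departs from its neighbours.

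**Step 2. Are the two mmol/L columns the same quantity?** With the assumed molar masses, mg/dL of urea nitrogen converts to mmol/L of urea at 10/28.014 = 0.357, and mg/dL of urea converts at 10/60.06 = 0.1665. Had the BUN column meant mmol of nitrogen atoms, its factor would be 10/14.007 = 0.714. The table's own ratio, 0.357/0.167 = 2.138, agrees with 60.06/28.014 = 2.144. Both columns are therefore mmol/L of urea.

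**Step 3. Compare the limits on that scale.**

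| Age band | BUN row (mmol/L) | Urea row (mmol/L) | Ratio |
|---|---|---|---|
| under 1 y | 8.568 | 7.014 | 1.222 |
| 1 to under 17 y | 12.852 | 10.02 | 1.283 |
| 17 y and over | 14.28 | 10.02 | 1.425 |

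The conflict is also present in conventional units. The urea limits expressed as BUN are 7.014/0.357 = 19.6 and 10.02/0.357 = 28.1 mg/dL, against stated BUN limits of 24, 36 and 40 mg/dL. A result of 11 mmol/L at age 10 lies above 10.02 and below 12.852, so it is markedly abnormal under the urea row and not under the BUN row.

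**Step 4. Creatinine.** At the factor of the other two rows, 1.2 × 88.4 = 106.08 umol/L. The stated 106.8 is 0.72 umol/L higher (0.72/106.08 = 0.7%) and corresponds to 106.8/88.4 = 1.208 mg/dL. It looks like a dropped zero. Only results above 106.08 and up to 106.8 umol/L change status. In whole umol/L, both limits first flag 107. In mg/dL to two decimals, the first value above the limit is 1.21, and 1.21 × 88.4 = 106.96, which both limits flag.

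**Step 5. Clearance at age 12.** The two footnotes exclude the boundary on both sides.

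- If age is in completed years, every 12-year-old is without an equation.
- If age is fractional, only age exactly 12.0 is missed.

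To see whether the choice of equation could matter, take an assumed 12-year-old of 150 cm and 40 kg. Schwartz is 150 × 0.55/creatinine. Cockcroft is (140 − 12) × 40/(72 × creatinine), times 0.85 for females.

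| Creatinine (mg/dL) | Schwartz | Cockcroft, male | Cockcroft, female |
|---|---|---|---|
| 0.7 | 117.9 | 101.6 | 86.3 |
| 1.2 | 68.8 | 59.3 | 50.4 |
| 1.5 | 55.0 | 47.4 | 40.3 |

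Of these three values, the equations fall on opposite sides of 50 mL/min only at the highest, 1.5 mg/dL.

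**The case against.** The strongest reply is that the BUN and urea conflict may never take effect. Section 8.3 restricts laboratory summaries to parameters planned in the protocol. If the protocol plans only one of the two, the other row is never used and the counts are internally consistent. This stands. A reader might infer that the reported incidence of renal abnormality will depend on how laboratories name the test, but the SAP does not say which analyte is collected, whether laboratories differ or whether results are harmonised. It is also right that the BUN and urea conversions contain no arithmetic error; what conflicts is the choice of limits.

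A reader might also take the 11 mmol/L example as a TEMA count. It is not: Section 8.3 additionally requires the value to have been normal at Baseline. The example shows a marked abnormality only.

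For clearance, a reader might infer that a full year of age is lost. The SAP does not state completed years for these equations. The 365.25-day year in the table's footer, the use of dates to obtain age at assessment in Section 8.3, and the months-divided-by-12 rule in Section 3.2.9 all point towards fractional age, under which almost nothing is missed. Whether clearance is a planned parameter is also not stated.

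Finally, laboratory parameters are listed as other safety variables in Section 2.3.2, all summaries are descriptive, and observed values and listings are produced whatever the flags say. That lowers the severity. It does not remove the inconsistency, since both the BUN and urea rows are kept with no rule of precedence.

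**Conclusion.** The point holds in a limited form. Table 12–2 contains three inconsistencies in its renal limits, of unequal weight.

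- **BUN and urea** carry most of it: limits 22%, 28% and 43% apart for one quantity. The effect on counts is conditional on results being held under both names or on laboratories differing in naming. That the columns are the same quantity rests on standard molar masses, supported by the ratio of the table's own factors.
- **Creatinine** is a definite conversion slip of 0.7% with negligible practical effect. It needs no outside figure.
- **Clearance at age 12** is a boundary gap whose size depends on an age convention that the SAP leaves open for these equations: one whole year of age, or almost nothing.

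Overall severity is minor to moderate. The primary safety variables (TEAEs, SAEs and withdrawals due to TEAEs) are untouched and no laboratory data are lost. What is at risk is the consistency of the flagged counts.

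**What to change.** Make three edits to Table 12–2 and its footnotes:

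1. Reconcile the BUN and urea rows so that each age band has one limit, the same mmol/L value in both rows with the mg/dL figures derived from it, and state that it applies whichever name the laboratory uses. The age bands and the inequality signs (at or above for BUN, above for urea) should be aligned as well. Which limit to keep is the sponsor's decision.
2. Correct 106.8 to 106.08 umol/L.
3. Make the two clearance age ranges adjoin, for example under 12 and 12 or over, which is how the ECG criteria in Table 8–2 handle that boundary. State whether age is fractional or in completed years.

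The cost is an update of the programmed lookup table. Counts of flagged values may move slightly in either direction, depending on the urea/BUN limit chosen.
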